In addition to surgical management of the tibia, the ipsilateral fibula will be assessed radiologically and decisions for surgical intervention will be incorporated into the operative strategy to stabilize the tibia. In cases where the fibula is intact, the fibula will undergo osteotomy with intramedullary fixation in order to shorten the fibula and prevent distraction by the intact fibula. In cases where the fibula was severely resorbed ("sucked candy" configuration on Xray), an osteotomy is not necessary and intramedullary fibular fixation is impossible to perform.

Patients will be immobilized with above-the-knee cast or spica cast for a minimum of 3 months post-operatively. Managing surgeons can decide on an individual basis whether a patient requires casting for longer than 3 months. After the cast is removed, patients will be permanently braced (24 hours per day) in a custom-made orthosis, either above-the-knee or below-the-knee, at the discretion of the surgeon. Radiographs of the lower leg and ankle will be performed at 6 weeks, 3, 6, 9, and 12 months after surgery at times corresponding to follow-up evaluations and cast changes.

Summary of Surgical Protocol:

- Tibial osteotomy
- Resection of pseudarthrosis tissue
- Fibular osteotomy if intact fibula
- Placement of intramedullary rod providing rigid fixation
 - Williams, Rush, or other type
- Ankle fixation at discretion of the surgeon
- Placement of iliac crest autograft at the surgical site
- If randomized to BMP-2 treatment group:
 - Reconstitution of BMP-2 in sterile water as per package instructions (at least 15 min before application) and applied to the collagen sponge(s).
 - A small INFUSE package (4.2 mg total BMP-2 and 2 sponges with concentration of 1.5 mg/ml) will be used for patients weighing < 30 kg
 - A Medium INFUSE package (8.4 mg total BMP-2 and 4 sponges, with concentration of 1.5 mg/ml) will be used for patients weighing ≥ 30 kg. INFUSE bone graft sponge is wrapped around the tibial osteotomy site and autograft.
- Incision is closed
- Above-the-knee or spica cast x minimum of 3 months

Rehabilitation Protocol

- All patients will be in an above-the-knee or spica cast for a minimum of 3 months
- Recommend no weight-bearing on affected leg for 3 months post-op
- Further cast immobilization may be used if the surgeon interprets the radiographs as having too little callus formation at the tibial pseudarthrosis site

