5.5 FUNCTIONAL ASSESSMENT: Ten Meter Timed Walk

The **timed 10 meter walk test** is a functional outcome measure that has been used extensively in the fields of rehabilitation medicine, neurology, and orthopaedics. In this well-validated, easily administered test, a 10 meter (32.8 feet) hallway is measured and marked, with starting line and end line. The patient is given instructions either to walk the distance at his/her normal, comfortable speed, or as quickly as safely possible. The walk is timed using a standard stopwatch, and results are recorded in seconds. The patient performs the test 3 times, and the mean value of the 3 trials is used as the result. Results from this test will be compared for individuals at baseline, 6 mos after surgery, and 12 mos after surgery, and will be used as a secondary outcome measure. The timed 10 meter walk is easy to perform in a clinic setting without special equipment such as a gait analysis lab. The test has been used extensively in studies of muscular dystrophy, spinal cord injury and cerebral palsy, and has been validated from ages 4 years through adults [Pirpis et al, 2003]. It has also been used as an outcome measure in a Phase 3 clinical trial for multiple sclerosis [Cohen et al., 2001]. A 20% change in walking speed is considered to be significant. The test can be performed while a patient is in a brace or other adaptive device. This test and other functional outcome measures have recently been reviewed extensively by the REINS committee, and based on its reliability and ease of use was recommended as a secondary outcome measure for NF trials assessing ambulation.

The 10 meter Timed Walking Test will be performed before surgery, and at 6 months and 12 months post surgery. The test can be performed with the leg braced, and any bracing or other assistive device will be recorded at each time point. The test will be performed 3 times, and the mean of the 3 times (in seconds) will be recorded as the final score at each visit.

Data will be entered into eDES at the clinical sites and sent electronically to the DMAC for subsequent analysis.

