6.1 Statistics and Feasibility

The primary objective of this study is to determine if there is improved healing of tibia in patients treated with BMP-2, compared to those treated with standard surgical protocol alone. The primary outcome for the study will be radiographic evidence of tibial healing 12 months after surgery, using the RUST criteria as described in section 6.4. For each cortex a score of 1, 2, or 3 will be given. A non-visible cortex will be given a score of 1. The cortex scores will be added together for a total score. We will define three levels of healing: RUST score of 4-7, score 8-9, or score 10-12. The primary analysis will be to compare the distribution of scores across the 3 groups (4-7, 8-9, 10-12) at 12 months post-surgery using a Wilcoxon Test. The proportion of patients achieving **complete healing** (score 9-12, with at least 2 evaluable cortices having a score of 3) will also be calculated and an exact 95% confidence interval computed.

Analyses based on the actual 4 – 12 scores will also be performed and compared between the two groups. In addition, the % of patients having a **successful outcome** (defined as RUST score of 9 or greater, with at least 2 evaluable cortices having a score of 3) will be compared between the two groups. Time to union will be compared between the two groups based on Xrays obtained at 5 points after surgery (6 weeks, 3 mos, 6, 9, and 12 mos).

Subjects who experience a serious treatment-related adverse event, refracture, or need for reoperation will be considered to be **study failures**. The proportion of failures within each group will be compared to assess safety success.

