As noted above we are likely giving up some power with this change to a Choice Design. Our assumption based on the current rate of declining to participate is that more patients will chose the BMP arm above the Control arm, but if we are incorrect, we would have adequate power (76% - 82%) if we were able to enroll 15-20 patients in the Control arm and 26 patients in the BMP arm. Even in a worse scenario that we were only able to recruit 10 patients to the Control arm + 26 to BMP, we would still have reasonable power of 65% to show a difference between the groups.

It is important to note that, although participants and providers in the Choice Arm will no longer be blinded to the treatment status of the participants, the Primary Outcome Measure (RUST score), will be determined by a group of 4 radiologists, all blinded to the treatment status of all participants.

Missing data: Reason for any missing 12 month radiographic data will be recorded by treatment group. Data from subjects missing the 12 month radiograph will not be included, unless multiple imputation is applied. Although minimal data are expected to be missing, multiple imputation technique will be used if 5% or more data are missing. This multiple imputation will replace the missing value with a set of plausible values that represent the uncertainty about the right value to impute. The multiply imputed data sets will then be analyzed by using the Wilcoxon Rank Sum Test for complete data on each and combining the results from these analyses. The variables used for the imputation will be RUST score at 6 months, age, prior surgery (Yes=1, No=0), and timed 10 meter walk at 12 months post-surgery.

Generalizability of the Results:

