6.6 EXPERIMENTAL DESIGN SCHEMA

APPENDIX I: Schedule of Evaluations

STUDIES TO BE OBTAINED	Pre-Study	Surgery	Post-Surgical Follow-up	Post-Trial FU
Informed Consent/ Assent	X			
Eligibility Checklist	X			
History and Physical Exam	X		6 w, 12 w (\pm 2 wks) 6 m, 9 m, 12 m (\pm 4 wks)	Annual
PE with vital signs (including T, P, RR, BP), Ht, weight	X		6 w, 12 w (\pm 2 wks) 6 m, 9 m, 12 m (\pm 4 wks)	
Performance Status (Karnofsky, Lansky scales)	X			
Adverse Event Reporting		X	6 w, 12 w, 6 m, 9 m, 12 m	Annual
CBC, differential, platelets	X		3 m, 12 m	
Total bilirubin	X			
Urinalysis	X		3 m, 12 m	
Urine Pregnancy ²	X		6 w	
Blood Electrolytes, BUN, creatinine, albumin, total protein, alkaline phosphatase, uric acid, SGOT, SGPT, GGT,	X		3 m, 12 m	
Serum calcium (ionized), magnesium, phosphorus	X		3 m, 12 m	
Serum Vitamin D	X		3 m, 12 m	
Bovine collagen I antibodies	X		6 w, 3m, (\pm 2 wks) 6 m, 12 m (\pm 4 wks)	Until negative
BMP-2 antibodies	X		6 w, 3 m, (\pm 2 wks) 6 m, 12 m (\pm 4 wks)	Until negative

Radiographs (PA/Lat) of the affected leg	X		6 w, 3 m, (\pm 2 wks) 6 m, 9 m, 12 m (\pm 4 wks)	Annual
PODCI (QOL scale)	X		6m, 12 m	
Faces pain scale	X		6 w, 3m, 6 m, 12 m	
10 Meter timed walk	X		6 m, 12 m	
OPTIONAL STUDIES TO BE OBTAINED (if participant consents)				
Blood for research studies		X		
Pseudarthrosis tissue		X		
Iliac crest bone		X		
Urine for research studies		X		

1. All studies to determine eligibility must be performed within 2 weeks prior to enrollment unless otherwise indicated below.
2. For females of childbearing age.

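### The imputation model for a missing 12-month RUST score leaves out the 9-month score and includes a walk test that is lost whenever the 12-month visit is missed

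*Combined protocol and SAP*

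**What the plan says.** Section 6.2 (Missing data) handles a missing 12-month film in two ways. Below a threshold the patient is dropped: "Data from subjects missing the 12 month radiograph will not be included, unless multiple imputation is applied". At or above it, "multiple imputation technique will be used if 5% or more data are missing". The imputation variables are fixed as "RUST score at 6 months, age, prior surgery (Yes=1, No=0), and timed 10 meter walk at 12 months post-surgery".

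Three other parts of the plan bear on that list.

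- **Walk schedule.** Section 5.5: "The 10 meter Timed Walking Test will be performed before surgery, and at 6 months and 12 months post surgery". The row for "10 Meter timed walk" in Appendix I agrees. There is no 9-month walk.
- **Film schedule.** Section 5.2: "Radiographs of the lower leg and ankle will be performed at 6 weeks, 3, 6, 9, and 12 months after surgery". Section 5.8 and Appendix I agree. Section 4.5 has the same four-member panel score all radiographs, and section 6.1 compares time to union "based on Xrays obtained at 5 points after surgery (6 weeks, 3 mos, 6, 9, and 12 mos". (Section 4.1 names the 9-month film in one sentence and omits it from a later list; every schedule of assessments includes it.)
- **Place of visits.** Section 4.2.2 lets families living more than 50 miles away have the 3- and 9-month films taken locally. The 6- and 12-month visits must be at a participating center.

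The plan does not say why the 9-month score is left out, or what happens when the 12-month walk is missing as well.

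**The concern.** An imputation model is useful to the extent that its predictors are observed in the patients being imputed and say something about the value they lack. On both counts the list can be improved.

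The 12-month walk belongs to the visit that produces the 12-month film. A patient who misses the visit has neither. The software can impute the walk jointly, but for that patient it then carries only what the other predictors already supply. What is left is a film six months old, age and prior surgery.

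The closest earlier reading of the same quantity, the 9-month score, is collected and scored but not used. It may well exist for a family that does not travel back at 12 months, because it can be taken near home. At stake is the precision of the imputed scores. If patients doing badly at 9 months are the ones who fail to return, so is their bias.

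**Working it through.** **Figures stated in the plan.** The plan gives no figure for the performance of the imputation, so there is none to reproduce on this point. Its power table (one-sided 0.05 Wilcoxon, 26 BMP against 5, 6, 7, 8, 9, 10, 15 and 20 controls: 46, 51, 56, 59, 62, 65, 76, 82%) recomputes to 46.4, 51.6, 56.1, 60.0, 63.4, 66.3, 76.7 and 82.7%. The proposed change does not alter that table.

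**Step 1: which predictors survive a missed 12-month visit?**

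| Variable | Time | On the list | Observed if the 12-month visit is missed |
|---|---|---|---|
| Age, prior surgery | baseline | yes | yes |
| RUST | 6 months | yes | yes, if that visit was kept |
| RUST | 9 months | no | yes, if that film was taken (local film allowed for distant families) |
| Walk | 12 months | yes | no |

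**Step 2: how often would the imputation be used?** Inputs: 36–52 patients with a goal of at least 15 controls and 26 BMP, so 41 (end of section 6.2); the 5% trigger (section 6.2); about 5% dropout (section 4.2.2), taken here as an independent 5% chance per patient.

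- Trigger: 0.05 × 36 = 1.8, so 2 patients; 0.05 × 41 = 2.05, so 3; 0.05 × 52 = 2.6, so 3.
- N = 36: P(at least 2) = 1 − 0.95^36 − 36 × 0.05 × 0.95^35 = 0.54.
- P(at least 3) from the same binomial: N = 41, 0.34; N = 46, 0.41; N = 52, 0.49.

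**Step 3: how much does the 9-month score add?** The documents give no between-visit correlation, so r = 0.6 to 0.8 is an assumption. Two structures are shown because the answer depends on the choice.

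- *Geometric decay* (r per three months): explained variance is r^4 from the 6-month film and r² from the 9-month film.
- *Equal correlation r at all visits*: r² from the 6-month film alone and 2r²/(1 + r) from both films.

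| r | Decay: 6-month | Decay: 9-month | Equal: 6-month | Equal: 6- and 9-month |
|---|---|---|---|---|
| 0.6 | 0.13 | 0.36 | 0.36 | 0.45 |
| 0.7 | 0.24 | 0.49 | 0.49 | 0.58 |
| 0.8 | 0.41 | 0.64 | 0.64 | 0.71 |

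**Step 4: illustration of bias.** A simulation assumed 26 against 15 patients, a 0.8 SD treatment difference, 10% of 12-month scores missing (4 of 41), worse 9-month scores more often missing, geometric decay, and a walk correlated 0.5 with the 12-month score. Age and prior surgery were not modelled. Entries are the mean error and root mean squared error of the predicted missing score, in SD units; a positive error is an overestimate.

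| Model | r = 0.6 | r = 0.8 |
|---|---|---|
| 6-month score, walk also missing | +0.42; 1.10 | +0.32; 0.91 |
| 6-month score, walk observed | +0.31; 0.95 | +0.26; 0.82 |
| 6- and 9-month scores, walk missing | +0.01; 0.90 | +0.01; 0.68 |

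The bias disappears in the last row because missingness was made to depend on the 9-month score, so this shows a mechanism and is not a forecast. The second row shows that the walk does help when it is observed.

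**The case against.** The strongest reply is that the trigger is a missing film, not a missed visit. Films travel on CD to a central panel and can be lost or unusable after an attended visit; the walk is then a contemporaneous predictor. This stands. A reader might infer that the walk is useless and should be replaced, but the documents do not support that.

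The 9-month film can be missing too: a patient lost before 9 months has none, and the plan gives no timing for dropout. This also stands, and is a reason to keep the 6-month score. It is no reason to ignore the 9-month score where it exists.

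Three further inferences are tempting and go too far.

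- *That the imputation is likely to be used.* At 5% missingness the probability is 34–54%, and the end of section 6.2 expects little or no attrition.
- *That the plan's own BMP series healed between the 6- and 9-month films.* In section 3.7 the smaller series averaged 6.4 months with a range from 3.7 to 8.1, so some healing preceded the 6-month film. The larger series averaged 9.5 months, after the nominal 9-month film.
- *That the walk is unavailable in children aged 2 to 3.* Section 5.5 says the test "has been validated from ages 4 years through adults", but a child operated on at 3 is about 4 at the 12-month walk, so mainly those entering at 2 are affected. Falling below the validated age is also not the same as having no result: Appendix I sets no age limit for the walk.

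Finally, section 6.2 (Analyses) plans a sensitivity analysis that scores inevaluable patients as failures. That gives a pessimistic check, though it defines evaluability by a section 10.5 that the table of contents does not list. It limits the consequence but leaves the imputation model unchanged.

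**Conclusion.** The point holds as an improvement that costs nothing. For a patient who misses the 12-month visit, one of the four listed predictors is missing by design, and the nearest same-scale reading is left out without a stated reason. The gain in explained variance is about 23 percentage points at either end of the range under geometric decay (13 to 36%, 41 to 64%). Under equal correlations it is 7 to 9 points (64 to 71%, 36 to 45%). Both rest on assumed correlations of 0.6 to 0.8.

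A reader might infer that the primary result is at risk. The documents do not support that: 2 or 3 patients are imputed at the trigger, the imputation may never be invoked, and no effect on type I error or power has been shown. The effect on the primary test is probably small.

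**What to change.** In section 6.2 (Missing data), add the 9-month RUST score to the imputation variables and keep the 6-month score, age and prior surgery. Keep the 12-month walk only as an auxiliary variable for patients who attended the visit but have no usable film, and say how it is handled when it is missing. The 6-month walk and the 3-month RUST score are optional; with 36 to 52 patients the model should stay small.

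The cost is about one sentence, with no new data, visits or patients and no change to sample size, power or alpha. It should be settled before any unblinded analysis. The list also does not name treatment group, although the imputed scores feed a between-group test. That is a separate question, but the same edit could settle it.

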Blinding: For subjects in the Choice Arm, all subjects, parents, and surgeons will of necessity be **unblinded** to the patient's treatment status of BMP versus no BMP. For those in the Randomized group, all subjects, parents, radiologists, data recorders, and (non-surgeon) site PIs will be **blinded** with respect to the treatment status of each participant. Only the surgeon and one study coordinator or OR tech (designated to deliver the device to the OR) at the site will be aware of the treatment status. If the surgeon is also the site PI, then that site PI will be unblinded. For the measurement of outcome measures, the radiology panel calculating the RUST score and all data recorders will be blinded to the treatment status of all participants. Therefore, **calculation of the primary outcome measure will be blinded for all participants, ensuring a non-biased measure for the primary study outcome.**

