Figure showing partial bridging and callus formation of all 4 cortices.

RUST score = 2+2+2+2 = 8

Implementation of the RUST scoring method as the sole criterion for tibial fracture healing will enable the same radiology review panel (RRP) of 4 individuals to score both prospective cases and historic controls. The total RUST point score range is 4 to 12. Additionally, information on functional status will be collected before surgery, and at each subsequent evaluation after surgery, as outlined in Johnston [2002] and [name] et al., [2010]. This includes status of the ability to walk with weight-bearing, use of orthotic support, presence of pain, point tenderness at the site, level of physical activity, additional surgery of the ipsilateral leg in addition to radiographic evidence of union, knee and ankle motion, foot position, leg-length discrepancy, and overall clinician satisfaction.

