All statistical analyses will be performed using SAS (version 9.3). All analyses are based on evaluable patients, as defined in section 10.5 with sensitivity analyses considering inevaluable patients as failures (scores 4-7). Summary statistics will be used to describe the study population (such as ranges, medians of ages, gender, baseline performance characteristics). The quality of life assessment in this study is based on the Pediatric Outcomes Data Collection Instrument, the PedsQL Pediatric Pain Questionnaire, and the 10 meter Timed Walk. From data collected on these questionnaires, scales are formed that measure domains such as global functioning, extremity and physical function, transfers and basic mobility, sports/physical function, happiness, and pain/comfort. These QOL and pain measures will be given pre-surgery, 3 months, 6 months, and 12 months after surgery. Since the scales are continuous, summary statistics will be generated for each measure at each time-point. The paired t-test will be used to look at changes in these measures from pre-treatment levels through 12 months. Longitudinal data analysis methods will be used to evaluate long-term changes in these measure using regression techniques employing mixed models.

In order to determine factors which may be prognostic for the success of BMP-2 treatment, we will perform Wilcoxon Rank Sum Tests to within each group to compare:

- 1) age \leq 8 years versus age $>$ 8 years
- 2) prior surgery versus no prior surgery; and
- 3) prior rhBMP-2 exposure versus rhBMP-2 naïve.

Regarding dose of rhBMP-2, those with 4.2 mg of rhBMP-2 implanted will be compared to those with 8.4 mg of rhBMP-2 implanted with respect to success rate using a chi square contingency table and with respect to number of adverse events using the Wilcoxon Rank Sum Test.

Relationships between quality of life measures and other variables (i.e., pain) will be investigated using correlational analyses. Performance status will be assessed using the Karnofsky Performance Scale. Generalized linear models will be used to evaluate changes in these scales and scores over time.

Early Stopping Rule

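### No rule makes a leg amputated before 12 months a failure in the primary RUST test: the analysis set points to a section that does not exist, and a missing film is dropped or imputed without treatment group

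*Combined protocol and SAP*

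**What the plan says.** **Analysis set.** Section 6.2 (Analyses): "All analyses are based on evaluable patients, as defined in section 10.5 with sensitivity analyses considering inevaluable patients as failures (scores 4-7". The contents list and the body both stop at section 6.6, followed by appendices. Section 5.9 lists criteria for removal from study (such as non-compliance with casting or bracing, or more than two missed visits) and off-study criteria, but does not connect either list to evaluability.

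**Missing films.** Section 6.2 (Missing data): "Data from subjects missing the 12 month radiograph will not be included, unless multiple imputation is applied". The switch is stated as "multiple imputation technique will be used if 5% or more data are missing". The model is stated as "The variables used for the imputation will be RUST score at 6 months, age, prior surgery (Yes=1, No=0), and timed 10 meter walk", the walk being the 12-month one. Neither treatment group nor event status is listed.

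**Failures.** Section 6.1: "Subjects who experience a serious treatment-related adverse event, refracture, or need for reoperation will be considered to be" study failures. Their stated use is separate from the primary test: "The proportion of failures within each group will be compared to assess safety success".

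**Non-visible cortex.** Section 6.1 gives such a cortex a score of 1. That rule needs a film and does not address an absent limb.

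**The concern.** A leg amputated before the 12-month visit has no tibial film. The plan does not name amputation under missing data, but its rule for a patient without a film applies as written. Below the 5% trigger the patient leaves the primary test. At or above it, the patient receives a score predicted from variables that know neither the treatment nor the amputation, and one of them, the 12-month walk, may itself be missing or altered after amputation. Either way, a definite treatment failure is not recorded as one in the primary comparison.

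The undefined term makes this worse. The 4-7 sensitivity analysis reaches amputees only if they are classed as inevaluable, and nobody can tell whether they are. It is also unsettled whether a patient removed under section 5.9 who has a 12-month film stays in the primary test. With perhaps 10 to 15 controls, one patient can matter, and the direction depends on the group in which the event falls. The rule should therefore be fixed before group results are seen.

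**Working it through.** **Inputs.** Section 6.2: controls 33/42/25% and BMP 15/20/65% in categories 4-7, 8-9 and 10-12; Wilcoxon rank-sum test, one-sided 0.05; 26 BMP devices and a minimum goal of 15 controls. Section 4.2.2: 36 to 52 patients. Numbers of amputations are assumptions.

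**1. The plan's own figures.** P(BMP better, ties counted half) = 0.33×(0.20+0.65) + 0.42×0.65 + ½×(0.33×0.15 + 0.42×0.20 + 0.25×0.65) = 0.5535 + 0.1480 = 0.7015, the 0.702 of the power table. Simulation with the tie-corrected test (400,000 replicates, 26 v 15) gives power 77%, against 76% in the table. The power figures are not in dispute.

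**2. When imputation starts.** 1/36 = 2.8%: dropped. 2/36 = 5.6%: imputed. 2/41 = 4.9%: dropped. 3/41 = 7.3%: imputed. One further missing film can therefore change the primary method.

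**3. Amputation scored 4-7 v excluded, 26 v 15.** Two versions are needed, because the documents do not say whether the planned 33% and 15% already include amputees.

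- *Added*: the stated number of patients are amputees, and the rest follow the planned distributions.
- *Within*: amputees are taken from the patients drawn into category 4-7 (expected 26×0.15 = 3.9 on BMP, 15×0.33 = 4.95 in controls).

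| Amputations | Added: scored v excluded | Within: scored v excluded |
|---|---|---|
| 1 BMP | 69% v 78% | 77% v about 84% |
| 2 BMP | 59% v 77% | 77% v 89% |
| 1 control | 83% v 77% | 77% v 70% |

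The levels differ between versions; the direction does not. With one amputation in each group the two rules nearly agree (added version: 76% v 75%).

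**4. What imputation could give an amputee.** If the listed predictors carried no information (the extreme case), the imputed score would follow the pooled distribution:

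- 4-7: (26×0.15 + 15×0.33)/41 = 8.85/41 = 21.6%
- 8-9: (26×0.20 + 15×0.42)/41 = 11.5/41 = 28.0%
- 10-12: (26×0.65 + 15×0.25)/41 = 20.65/41 = 50.4%

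The chance of 8 or above is then 28.0 + 50.4 = 78.4%. A low 6-month RUST would reduce it. A score of 8 or above is also not the plan's definition of healed, which is 9-12 with at least two evaluable cortices at 3.

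**5. Omitting treatment group for films missing at random.** With a fraction m imputed from the pooled distribution in both groups, P becomes 0.5 + (0.7015 − 0.5)×(1 − m). At m = 3/41: 0.5 + 0.2015×0.927 = 0.687. This is the largest shrinkage, because 6-month RUST carries some treatment information.

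**The case against.** **Amputation is not ignored everywhere.** A reader might infer that it counts only in the 4-7 sensitivity analysis. The documents do not support that. Section 6.1 counts need for reoperation as a study failure, and section 3.7 counts four amputations among patients needing a second surgery, so an amputee plausibly enters the safety comparison. This stands, but that comparison is not the primary test.

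**Events before 12 months may be few.** Section 5.7 foresees a second procedure for clear non-union after 12 months, and section 4.1 follows amputation and re-fracture in the long-term registry. This stands too. The pilot figures in section 3.7, 4 of 24 rod/graft patients (17%) and 3 of 23 treated with BMP-2 (13%), have no 12-month limit, and the 23 include 7 patients without NF1. They show that amputation occurs, not how often within the trial window.

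**The decision to amputate is not blinded.** Section 4.2.3 says "calculation of the primary outcome measure will be blinded for all participants", but the surgeon knows the treatment in both arms and families know it in the Choice Arm. Scoring amputation 4-7 brings an unblinded decision into the primary score. This is a real cost and calls for a sensitivity analysis.

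**Films after refracture or reoperation.** A reader might go further and call the silence on these films an error that inflates the false-positive rate. The documents do not support that. Section 5.3 describes "Implementation of the RUST scoring method as the sole criterion for tibial fracture healing", so reading the film as it stands is a coherent choice. When events are equally common in both groups and later films read as 8-9 or as the control distribution, simulated error stays at 5.0%. Error of 15-18% needs event rates of 5% in controls v 20% on BMP, a contrast no passage supports. Section 3.7 gives mean times to union of 9.5 months with BMP-2 and 16 without, so a film soon after revision may still read 4-7. What remains is a request to state the rule.

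**Conclusion.** The concern holds for the primary RUST test. The analysis set is undefined because its reference leads nowhere; the contents list shows that this is not a redaction. As written, the missing-film rule drops an amputated leg or lets it be imputed at 8 or above.

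The size is illustrative, because the documents give no amputation rate before 12 months. At 26 v 15, the gap in power between scoring and excluding one amputation is about 6 to 9 points; for two on BMP it is 12 to 18. The levels depend on whether amputees are added to or taken from the planned 4-7 share. In both versions excluding a BMP amputee favours BMP and excluding a control amputee works against it, so a uniform bias toward BMP should not be inferred. Omitting treatment group from the imputation is a defect of small size: P(BMP better) falls from 0.702 to no less than 0.687 with 3 of 41 films missing.

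This should be fixed before any comparison of RUST by group.

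**What to change.** 1. Delete the reference to section 10.5. Define the primary set as all patients who had the study surgery, in their assigned or chosen group. Keep patients removed under section 5.9 when a 12-month film exists.
2. Score amputation of the study leg before the 12-month film as category 4-7 in the primary test, neither excluded nor imputed. Report a sensitivity analysis without this rule, because the decision to amputate is not blinded.
3. Add treatment group to the imputation model. Impute only films missing for other reasons, and keep the existing 4-7 sensitivity analysis for them.

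Secondary request, not an error: before group results are seen, state whether films taken after refracture or reoperation are read as they stand, and report a sensitivity analysis scoring those patients 4-7. Use event data already collected, and do not give clinical records to the radiology panel, which under section 4.5 receives films with study identifiers only.

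The cost is SAP wording and a few extra analyses. No new data are needed: section 6.2 already records the reason for a missing film, and section 5.8 already documents intervening surgeries. The one real price is the unblinded element in item 2, which its sensitivity analysis makes visible but does not remove.
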